- Step 2 (optional): Explore adding other covariate terms to the Step 1 model (for example, but not limited to, Age, Gender, Dose per kg, Blood eosinophil levels). Use expert judgment and changes in DIC to determine final model to take to Step 3. Include any Step 2 models in the listing output and add the associated DIC / changes in DIC values to those produced in Step 1.
- Step 3: For the finally selected model use appropriate combinations of the model parameters (back transforming the combination if necessary) to obtain posterior distributions for the quantities of interest described in the Model Results Presentation. Binary flag variables can be used to evaluate the probability statements, by tracking the instances of the desired event happening over each MCMC iteration and taking the mean of the flag variable as the probability.

For example, if Model 3 is selected then the posterior distribution for the Placebo can be

Primary Statistical Analyses

obtained from adding model parameters Intercept + Treatment[#1] Note: The baseline term is centered and drops out of the expression since it is evaluated at its centered mean of zero; similarly the random centre effect also has mean zero.

The treatment difference (Active – Placebo) would be –Treatment[#1] because the Treatment[#2] parameter is constrained to be zero and the other model terms cancel out.

The Percentage attenuation would be $100 * (1 - (\text{Intercept} / (\text{Intercept} + \text{Treatment}[\#1])))$

The SAS syntax for setting up indicator flags to obtain the probability of any percentage attenuation is Myflag = (pctann > 0); where pctann is the variable storing the Percentage attenuation.

Programming technical note(s): i) Use of flag variables may result in several error/warning messages in the SAS log (for example, but not limited to, warnings about large autocorrelation and/or zero variance); which should be reviewed but may be safely discounted – if in doubt consult the study statistician. ii) To facilitate summary outputs where results from multiple models are displayed simultaneously (large) intermediate datasets from Proc MCMC may need to be stored to ensure consistency (i.e. no differences due to simulation error between model re-runs). Suitable naming conventions should be used to label these files which group related items together.

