<h3>Model Results Presentation</h3> 
 • The information derived for each of the three visits would be similar to that presented for the Primary Statistical Analysis (see Section 7.1.2) (i.e. focus on comparison of GSK2245035 vs Placebo within each visit; except that at FUV2 and FUV3 the additional probability statements for the percentage attenuations exceeding AZ estimates are not required). 				

Exploratory Statistical Analyses: Repeated measures version LAR Primary analysis model	
Sensitivity and Supportive Statistical Analyses	

 • By subject time profiles of the derived endpoints, split by treatment arm with separate identifiers (plotting symbols) for the allergen exposure strata • If data permit, the repeated measures equivalent of the models exploring the blood eosinophil levels would be attempted (see Sensitivity analysis in Section 7.1.2). This would also make the simplifying assumption that allergen exposure terms are not required and build up the equivalent of models R1-R3 using (log transformed and visit centered) blood eosinophil values in place of the allergen exposure term(s). Predictions would be made for the treatment means and differences at each visit using the same set of eosinophil values as Section 7.1.2. 	

Exploratory Statistical Analyses: EAR Repeated measures model	
Endpoint(s)	

 • EAR: minimum <change from saline baseline> FEV₁ between 0-2 hours following allergen challenge at the three follow up visits (i.e. FUV1, FUV2 and FUV3). • EAR: weighted mean of <change from saline baseline> FEV₁ between 0-2 hours following allergen challenge at the three follow up visits (i.e. FUV1, FUV2 and FUV3). • Note: Text in <> added for clarity, since the wording in the protocol and objectives is familiar to clinical experts in the field, but may be confusing given there are also absolute FEV₁ values measured at those times too. 	
Model Specification & All other details	

 • As per LAR repeated measures analysis described in this section; including the sensitivity analyses exploring blood eosinophil levels as a covariate. 	

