T&E procedure	"Informal" description / rationale for samples	Matrix	Functional Categories	Vendor (Δ)	Analyte(s)	Comments	
						Anticipated Placebo profile	Characteristics of Successful drug effect
Sputum induction and processing for BAC associated sample collection	Changes over time (Pre-BAC timepoint)	Cell Pellet	Sputum differentials	BIOSPIT	Absolute values (Cells/g sputum) and % (of Total Non-Squamous Cells) for: Eosinophils, Neutrophils, Lymphocytes, Macrophages, Bronchial Epithelial Cells & Total Non-Squamous Cells	BAC may increase Sputum EOS (Absolute values and/or %) relative to Placebo for i) Baseline (Pre-BAC) or ii) BAC induced increase (Post/Pre ratio)	Reduced Sputum EOS (Absolute values and/or %) relative to Placebo for i) Baseline (Pre-BAC) or ii) BAC induced increase (Post/Pre ratio)
	Direct BAC changes (Post Vs Pre BAC)	PBS Wash	Inflammatory mediators	GSK (Stevenage)	IL-5, IL-13 Conditional: IL-16, IL-33, TSLP, Eotaxin, MDC, TARC, ECP	BAC may increase inflammatory mediator levels e.g. IL-5 & IL-13	Reduced sputum TH2 mediators (IL-5 & IL-13) relative to Placebo for i) Baseline (Pre-BAC) or ii) BAC induced increase (Post/Pre ratio)
		Cell Pellet RNA	Inflammatory gene expression	Expression Analysis	Affy CHIP Note: Data generation conditional on sufficient cells remaining in	BAC may increase inflammatory gene expression	Reduction or change in nature of BAC induced gene expression

T&E procedure	"Informal" description / rationale for samples	Matrix	Functional Categories	Vendor (Δ)	Analyte(s)	Comments	
						Anticipated Placebo profile	Characteristics of Successful drug effect
					sample and sufficient sputum producers		(Post/Pre) or the Baseline (pre BAC) gene expression
Laboratory assessments (haematology only)	Blood (WBC & Differentials): Changes over time (Pre-BAC timepoint) Direct BAC changes (Post Vs Pre BAC)	Blood	Blood WBC and differentials	Q2	Absolute values (Cell counts) and % (of Total WBC) for: Eosinophils, Neutrophils, Lymphocytes, Monocytes, Basophils, & Total WBC Note: Neutrophils refers to Total Neutrophils (Segs + Bands), as described in dataset manager codelists	Blood EOS may increase (either Absolute counts or %) after the BAC	Reduction in (Pre-BAC) blood EOS (as absolute count or %) from SV and/or Reduction in BAC induced increase in blood EOS after treatment compared to pbo

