11.9 Appendix 9: Examination of Covariates, Subgroups & Other Strata

11.9.1 Handling of Covariates, Subgroups & Other Strata

- The following is a list of covariates that may be used in descriptive summaries and statistical analyses, some of which may also be used for subgroup analyses.
- Additional covariates of clinical interest may also be considered.
- If the percentage of subjects is small within a particular subgroup, then the subgroup categories may be refined prior to unblinding the trial.
- If the category cannot be refined further, then descriptive rather than statistical comparisons may be performed for the particular subgroup.
- To avoid parameter estimation problems caused by the small sample size (i.e. empty cells in the possible combinations of centre, treatment and allergen exposure) the default approach (unless specified otherwise) for fitting centre in statistical models is to handle it as a random effect (Normally distributed with mean zero and a SD appropriate to the endpoint). Where possible historical data would be used to form a weakly informative prior for the SD, with the specific value described in the corresponding RAP section. If historical data are not available then the distribution for the random centre effects would use a SD value of 1000.
- For analyses without repeated measures over visit, the output from fitting three nested models (M1-M3) to each statistical analysis should be available (e.g. listing form); but inferences (summary tables and figures) would be produced from the final chosen model only. The three models represent possible combinations of centre (fitted as a random effect), treatment and allergen exposure status (fitted as fixed effects). The models may include other terms appropriate to the analysis, but any further covariate exploration activity would start using the selected model (M1, M2 or M3) as its base:
 - **M1:** Centre + Treatment + Allergen Exposure + Treatment*Allergen Exposure + <other terms>
 - **M2:** Centre + Treatment + Allergen Exposure + <other terms>
 - **M3:** Centre + Treatment + <other terms>

Where Treatment = “Placebo” or “20ng GSK2245035”, Allergen Exposure = “Presumed allergen” or “Unknown allergen” and Centre is the random effect drawn from the $N(0, SD)$ distribution.

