- The DIC criteria (which may be overruled by expert judgement) would be used to select from Models M1-M3 (see Section 11.11.1). To aid review DIC values from models M1 to M3 should also be summarised in one location in the listing. Examples of expert judgement would be rejecting model M1, even if the DIC

suggested otherwise, if the effect size was deemed to be too small to be clinically important/relevant (i.e. differences in the point estimates for the presumed and unknown allergen exposure responses are clinically unimportant). Other examples of expert judgement include making an overarching decision on the model structure based on all endpoints of a similar nature (e.g. choosing a model form (M1, M2 or M3) for both primary endpoints, or for all serum biomarkers measuring TLR7 induction).

- An analogous set of three models should be used when comparisons of treatment within multiple visits are of interest:
 - **R1:** Centre + Treatment + Visit + Allergen Exposure + Treatment*Visit + Allergen Exposure*Visit + Treatment*Allergen Exposure + Treatment*Allergen Exposure*Visit + <other terms>
 - **R2:** Centre + Treatment + Visit + Allergen Exposure + Treatment*Visit + Allergen Exposure*Visit + <other terms>
 - **R3:** Centre + Treatment + Visit + Treatment*Visit + <other terms>
- If any of the models M1-M3 (or R1-R3) cannot be fitted then the formal process to select models described above is not possible and the default approach should be to use the simplest model form that has acceptable model convergence.

Category	Covariates and / or Subgroups
Centre	One level per site contributing evaluable data to the analysis. Sites may be grouped by country for display purposes. If pooling of centres is deemed necessary the strategy would be to pool centres within the same country before attempting to pool centres over different countries.
Country	Currently planned to be either "UK" or "Germany" but other countries may be utilised.
Allergen Exposure	"Presumed allergen" or "Unknown allergen"
Blood Eosinophil Levels (Cells/mL)	Although the planned statistical modelling will fit this term as a continuous covariate the following categorical variables may be derived based on 
 i) Baseline (SV2) Blood Eosinophils: <150 Cells/mL and >= 150 Cell/mL ii) BAC visit Blood Eosinophil Levels: <150 Cells/mL and >= 150 Cell/mL

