Sputum Eosinophil Levels (%) Note: Only if data are available	Although only derivable for subjects/timepoints where sputum samples were produced and were viable the following variables should be created for use as potential categorical covariates based on 
 i) Baseline (SV2) Sputum Eosinophils: <= 2% and > 2% ii) BAC visit Sputum Eosinophils: <= 2% and > 2% iii) Baseline (SV2) Sputum Eosinophils: <= Median of Observed values and > Median of Observed values

Category	Covariates and / or Subgroups
	iv) BAC visit Sputum Eosinophils: <= Median of Observed values and > Median of Observed values
FeNo (Ppb)	Potential categorical covariate based on i) <= 25 ppb and > 25 ppb

11.10 Appendix 10: Multiple Comparisons & Multiplicity**11.10.1 Handling of Multiple Comparisons & Multiplicity**

Due to the extensive use of a Bayesian framework and the early phase / exploratory medicine nature of this study there will be no explicit multiplicity adjustments.

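### SAP 11.9.1 permits BAC-visit eosinophils, which treatment may change, as covariates or subgroups; models of the treatment effect should be limited to screening values

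*SAP*

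**What the plan says.** SAP 11.9.1 gives a "list of covariates that may be used in descriptive summaries and statistical analyses", "some of which may also be used for subgroup analyses". For blood eosinophils it has two separate items, each cut at 150: the SV2 baseline value, and "BAC visit Blood Eosinophil Levels". For sputum, if data are available, the instruction is firmer: "the following variables should be created for use as potential categorical covariates based on" the baseline value and also "BAC visit Sputum Eosinophils", each cut at 2% and at the observed median.

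Two LAR analyses mention eosinophils without fixing them to baseline:

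- Step 2 of the primary model (SAP 7.1.2) may add terms such as "Age, Gender, Dose per kg, Blood eosinophil levels".
- The repeated-measures eosinophil model (SAP 8.1.2) is built "using (log transformed and visit centered) blood eosinophil values in place of the allergen exposure term(s".

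Table 12 (SAP 8.4.1) lists among the features of a successful drug effect "Reduction in (Pre-BAC) blood EOS (as absolute count or %) from SV", a smaller rise in blood eosinophils after the challenge, and lower sputum eosinophils. Table 13 marks a decrease as the wanted direction in both matrices.

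Other text points the other way. M1-M3 and R1-R3 have no eosinophil term. The FUV1 eosinophil sensitivity model in 7.1.2 uses the SV2 value as a continuous covariate, and the same paragraph assigns the 11.9.1 blood categories to descriptive tables. No section excludes post-randomisation covariates.

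**The concern.** The follow-up challenges take place 1, 4 and 12 weeks after the last dose, so eosinophils measured there come after randomisation and after the full course. The plan hopes treatment will lower them, and it analyses them as outcomes in 8.4.2.1. A model that also conditions on them no longer estimates the total effect of assignment on LAR. It removes whatever part of the effect runs through eosinophils. If something unmeasured drives both eosinophils and LAR, it also adds confounding that randomisation had excluded. Comparing arms within BAC-visit eosinophil subgroups has the same defect.

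The stake is highest in Step 2. Step 3 takes the posterior probabilities from the finally selected model, and the protocol's success rule is a posterior probability of any attenuation above 0.7. A post-randomisation term retained in Step 2 would therefore carry into that criterion.

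The variable is also loosely defined. Blood is sampled before and 24 hours after each challenge (SAP Table 11), and 11.9.1 does not say which sample is the BAC-visit value. The 24-hour sample is taken after the 4-10 hour LAR window has closed.

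**Working it through.** **1. The plan's own figure.** Inputs from protocol Table 2 (unweighted means over the eight studies): minimum LAR 1.0504 L, variance 0.2329; weighted mean LAR 0.6558 L, variance 0.1642. Assumed attenuations are 18% and 27%, with 20 per arm. With a flat prior, the 0.7 rule is close to a one-sided test at 0.30, so

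P(success) ≈ Φ(effect / √(2 × variance / 20) − 0.524).

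- Minimum: effect 0.18 × 1.0504 = 0.189 L; SE √(2 × 0.2329 / 20) = 0.153; Φ(1.239 − 0.524) = 76.3%.
- Weighted mean: effect 0.27 × 0.6558 = 0.177 L; SE 0.128; Φ(1.382 − 0.524) = 80.4%.

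Weighting both mean and variance by degrees of freedom gives 76.8% and 81.0%. The protocol states about 78% and 81%, so the figures reproduce within 2 points. Nothing here disputes them.

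**2. Illustration for minimum LAR.** From Table 2: effect 0.189 L; df-weighted variance 0.188 (SD 0.434 L). Assumed, because the documents give no values: drug lowers eosinophils by 25%; SD of log2 eosinophils 0.9; within-arm correlation with LAR 0.4.

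- Reference: SE √(2 × 0.188 / 20) = 0.137; Φ(1.378 − 0.524) = 80%. This pairs an unweighted mean with a df-weighted variance, hence 80% and not 76-77%.
- Shift in eosinophils: −log2(0.75) / 0.9 = 0.415 / 0.9 = 0.461 SD.
- Effect removed by a continuous covariate: 0.4 × 0.434 × 0.461 = 0.080 L, leaving 0.189 − 0.080 = 0.109 L.
- Adjusted SE: 0.137 × √(1 − 0.4²) × √(1 + 0.461² / 4) = 0.129. The covariate explains some variance but is now correlated with treatment.
- P(success): Φ(0.109 / 0.129 − 0.524) ≈ 62%.

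The BAC-visit items in 11.9.1 are categorical. Simulating 20,000 trials with a median split in place of the continuous value leaves about 0.14 L and 69%.

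**3. Range over the assumptions.**

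| Reduction, correlation | Continuous | Dichotomised |
|---|---|---|
| 10%, 0.2 | about 0.175 L, 77% | about 0.18 L, 78% |
| 25%, 0.4 | 0.109 L, 62% | about 0.14 L, 69% |
| 40%, 0.5 | 0.012 L, 33% | about 0.08 L, 52% |
| none, any | 0.189 L, no loss | 0.189 L, no loss |

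Eosinophils need not act on LAR for this to matter. With no such path, but an unmeasured common cause and a 0.5 SD drug effect on eosinophils (assumed standardised paths), the adjusted estimate kept 78% of the true effect (continuous) or 86% (dichotomised).

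**4. Would model selection screen the term out?** Not by itself. DIC rewards covariates that predict LAR, and the SAP says DIC approximates AIC under its non-informative priors. In simulated trials of 20 per arm, adding an eosinophil term improved AIC by more than 2.5 (beyond the SAP's range for rival models that deserve consideration) in about 70% of trials at correlation 0.4, and in about 21% at 0.2.

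**The case against.** The strongest reply is that no specified LAR model clearly uses a BAC-visit eosinophil value. Section 11.9.1 is a generic, permissive list that does not mention LAR. The default models carry no eosinophil term, and the one fully specified eosinophil model uses SV2. The blood categories have a stated descriptive purpose, and no listed efficacy display puts sputum eosinophils into an LAR model. All of this stands. A reader might infer that the planned primary analysis is biased; the documents do not support that.

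Step 2 is optional, and its other examples are not treatment outcomes. Harm requires that Step 2 is run, that the BAC-visit value is preferred to SV2, and that the term is retained. Outputs from M1-M3 must be listed, so the unadjusted result stays visible. This stands too, but 11.9.1 draws inference from the final model only, and no instruction tells the statistician to reject a post-randomisation term.

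In the repeated-measures model, centring by visit could mean time-varying values. It could equally mean the SV2 value centred over the subjects contributing at each visit, since the paragraph refers back to 7.1.2. That is an ambiguity to resolve, not a demonstrated error.

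Finally, Table 12 describes what success would look like, not an established effect, and SAP 8.4.2.1.2 is uncertain whether blood eosinophils would fall or merely rise less. The bias is therefore conditional.

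**Conclusion.** The point holds as a permitted route to bias. Section 11.9.1 explicitly names post-randomisation blood and sputum eosinophils, distinct from baseline, as usable covariates or subgroups, while Tables 12 and 13 treat their reduction as a drug effect. Step 2 and the repeated-measures eosinophil model leave the time point open. M1-M3, R1-R3 and the named FUV1 sensitivity model are unaffected.

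The size cannot be obtained from the documents. The fall from about 80% to 62% or 69% rests on the assumed reduction, correlation and eosinophil SD. The worst case of 0.012 L and 33% applies only to a continuous covariate at the extreme of the assumed range and should not be read as the expected loss. The direction is not in doubt if the drug lowers eosinophils and lower eosinophils go with a milder LAR: the adjusted effect is then too small as an estimate of the total effect.

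**What to change.** 1. In 11.9.1 and Step 2 of 7.1.2, state that any model or subgroup estimating the treatment effect on LAR or EAR uses pre-dose screening eosinophils only: for blood, the SV2 sample before the challenge; for sputum, the screening sample before the challenge.
2. In 8.1.2, state that the repeated-measures eosinophil models use that same baseline value at every visit.
3. Keep BAC-visit eosinophils as outcomes, in descriptive tables, or in analyses labelled mediation or exploratory. State that these do not inform the treatment effect or the 0.7 criterion, and say whether the pre-challenge or 24-hour sample is meant.

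The cost is a few lines of SAP text. The screening samples are already scheduled, and no sample size or stated operating characteristic changes.

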11.11 Appendix 11: Model Checking and Diagnostics for Statistical Analyses

11.11.1 Statistical Analysis Assumptions

Endpoint(s)	
 • All which are modelled using a Bayesian framework
Analysis	
 • Bayesian (Proc MCMC)

General Considerations for Bayesian Analyses (PROC MCMC):

The following points are for guidance and illustration and do not guarantee a successful model convergence. They cannot cover all eventualities and do not remove the requirement to do what is best for the specific set of observed data being modelled.

Priors:

Unless otherwise specified the following would be the default approach to selecting prior distributions:

- Non-informative priors of the form $\text{Normal}(0, \text{Var}=1\text{E}6)$ would be assigned to each fixed effect in the proposed statistical model.
- Non-informative Inverse-gamma priors of the form $\text{IGamma}(0.001, 0.001)$ would be assigned to stand-alone variance parameters that are not expected to take values near zero (e.g. for the residual variance rather than a random effect variance component)
- For stand-alone variance parameters that may take values close to zero a non-informative prior of the form $\text{Uniform}(0, \text{XXX})$ may be assigned for the SD
- For repeated measures models non-informative Inverse-Wishart priors will be assigned for the Variance Covariance matrix (VCV). They would use degrees of freedom equal to the dimension of the VCV matrix and an Identity matrix (of the same dimension).
- If there are issues with those variance parameters then the Identity matrix may be replaced with a diagonal matrix that uses best guesses for the residual variance at each repeated measure time point (or the residual estimates from fitting simple models)
- It is good practice to ensure that each prior distribution is visualised to ensure it appears sensible and allows clinically plausible response values, whilst not allowing impossible values to be drawn with high probability and that if it is intended to be non-informative it is doing so over the region of the likelihood function.

Note: There is no requirement to formally report these visualisation outputs.

Initial Values:

Unless otherwise specified initial parameter values of zero would be used for the fixed effect parameters and for remaining model parameters initial values may be drawn at random from their respective prior distribution. If model converge is problematic then alternative estimates, more suited to the particular dataset being modelled, may be used (for example, these could be based on visual inspection of the raw data and/or parameter estimates from fitting simpler models).

Checking Convergence and Other Diagnostics:

The key model diagnostic output is the MCSE/SD ratio for each parameter:

- Adequate values for the number of MCMC samples / thinning / number of burn in

samples should be chosen to ensure that the **MCSE/SD for the key parameters is below 0.01** (e.g. key parameters those associated with treatment, or as pre-specified comparisons of interest) in each final model.

- For other model parameters, try to get the **MCSE/SD values as close to 0.01 as possible**, but if there is significant autocorrelation then values **below 0.05 would be considered acceptable**.
- In addition, the number of tuning units and maximum number of tuning iterations may be increased to find a better multivariate normal approximation to the parameters, which in turn may reduce the MCSE/SD values
- Where possible the code should be written to allow the SAS compiler to identify and use conjugate sampling, since this can greatly reduce the corresponding MCSE/SD values
- Models selected with MCSE/SD values above 0.01 (for key parameters) or 0.05 (for other parameters) would need a brief remark/justification added to the QC log and/or CPSR to clarify why it was not possible to reach the targets and why it is believed the subsequent model still has utility.

Use of the default SAS PROC MCMC diagnostic plots should be made and where possible:

- Autocorrelation should decline rapidly and show no oscillation patterns
- Worm plots should show the chain appears to be stationary and mixing, i.e.
 - Constant mean, constant variance
 - Moving around the parameter space freely (not getting “stuck” at similar values for a large number of iterations before moving on again)
 - Moving rapidly between extremes
- The posterior density should look reasonable for each parameter (e.g. for posterior parameters expected to follow a normal distribution the density plot should not appear bi-modal, but for parameters acting as binary flags then bi-modal is acceptable)

Use of a bespoke GSK utility macro “%ScatterHist” is encouraged to examine correlation structures between relevant posterior parameters (and/or parameters in each PARMS block). This can provide information about what potential issues may be and also what corrective action(s) may be worthwhile attempting.

(SAS macro code of the most up to date version including any refinements would be available from GSK internal training course materials – modifications may be made to improve axis scales and legibility as required).

Possible corrective actions:

Possible corrective actions include but are not limited to:

- Moving parameters (or combinations of parameters) onto separate PARMS statements (to form blocks that are updated independently in the MCMC algorithms)
- Increasing the number of MCMC draws from the posterior distributions
- Increasing the length of the burn in period
- Increasing the thinning parameter (to reduce the autocorrelation)
- Centring covariates (to reduce correlations between the posterior parameters)
- Re-parameterising the model (e.g. using log-normal prior distributions to stop values being

- sampled that are below zero)
- Re-scaling the parameters (e.g. if one parameter takes values orders of magnitudes different to the other model parameters then dividing it by a suitable constant but back transforming the rescaled parameter prior to its use in any subsequent manipulations)
- Visualising the likelihood function of the dataset to determine if there are more appropriate starting estimates (or profiled versions of the likelihood for subsets of model parameters where difficulties are being encountered if it is a high dimensionality problem)
- Consulting with internal GSK experts to resolve the issues

Model selection / Criteria for assessing covariates:

The following is a “rule of thumb” only; the study statistician’s expert judgment based on the observed data / context of the endpoint / scientific & biological rationale for including a covariate may override this:

- Changes in Deviance Information Criterion (DIC) may be used to compare models that have been fitted to the same dependent variable (endpoint). In general the model with the lowest DIC would be preferred; although the simpler models would be selected if the differences in DIC were sufficiently small (see below for guidance on what constitutes sufficiently small).
- Since most of the proposed MCMC modeling is undertaken using non-informative priors the DIC approximates Akaike Information Criteria (AIC) and therefore the AIC “rules of thumb” may be used to guide the selection as follows: Suppose there are R candidate models. Let $DIC_1, DIC_2, \dots, DIC_R$ be the Deviance Information Criteria for each model and let DIC_{min} be the minimum of these values.
- “*Models receiving DIC within 1–2 of the ‘best’ (DIC_{min}) deserve consideration, and models within 3–7 have considerably less support*” ([Spiegelhalter](#), 2002). These boundaries have been modified so that there are no gaps as follows: if the difference in DIC is < 1 then choose the simpler model, refine the “deserve consideration” range to be $1 < \text{Diff DIC} \leq 2.5$ and the “less support” range to be $2.5 < \text{Diff DIC} \leq 7$. Models receiving DIC in excess of 7 from DIC_{min} should not be considered unless there is sufficient scientific/biological rationale for favoring the additional model / covariates.

Utilising the posterior distributions:

- In the relevant statistical analysis sections pre-specified quantities of interest are supplied to be obtained from the posterior distribution (e.g. [Table 14](#)). These lists should not be considered exhaustive and may be amended as further information becomes available (for example, but not limited to, if competitors publish results that set a new benchmark then GSK2245035 may be compared to that benchmark by adding it to the list of cut points). Results from any additions should appear after the pre-specified quantities in the corresponding outputs.
- Equi-tail credible intervals should be used, since they are invariant under transformation of the parameter space (unlike Highest Posterior Density).
- In addition, truncation of the x-axis ranges for posterior distributions may be necessary if there are a small number of extreme value posterior samples that would otherwise inhibit interpretation of where the bulk of the distribution lies. Appropriate footnotes should indicate whether axes have been truncated and give an indication of the level of truncation (e.g. 5 values are truncated, or less than 0.1% of posterior samples are truncated).

- To facilitate review the posterior distributions may be grouped into lattice plots to move more towards the “big picture on one page”. SAS PROC MCMC uses the density statement in GTL to produce its internal diagnostic figures from the dataset of posterior samples; hence it is possible to re-produce and add customisations to those density plots (such as displaying them in a lattice layout); although it may require on the fly combinations of several of the temporary datasets that store the individual MCMC samples.

